## 1. OBJECTIVES

### 1.1 Study Design

This is an open-label phase II study to evaluate the safety and efficacy of ramucirumab in patients with advanced carcinoid tumors.

### 1.2 Primary Objectives

- To assess the progression-free survival duration of patients with advanced, progressive carcinoid tumors treated with ramucirumab in combination with somatostatin analog therapy.

### 1.3 Secondary Objectives

- To determine the safety and tolerability of ramucirumab in combination with somatostatin analog therapy in patients with advanced carcinoid tumors.
- To assess the overall radiographic and biochemical response rate associated with ramucirumab in combination with somatostatin analog therapy in patients with advanced carcinoid tumors
- To assess the overall survival duration of patients with advanced, progressive carcinoid tumors treated with ramucirumab in combination with somatostatin analog therapy.

## 2. BACKGROUND

### 2.1 Overview of Neuroendocrine Tumors

Neuroendocrine tumors (NETs) are a heterogeneous group of malignancies characterized by variable but most often indolent biologic behavior. Well-differentiated NETs can be broadly classified as either carcinoid or pancreatic NET.

The treatment of advanced NET has undergone a rapid evolution in recent years. In addition to controlling symptoms related to hormone hypersecretion, somatostatin analogs have also been shown to control tumor growth. In the PROMID trial, patients with advanced small bowel carcinoid tumors receiving octreotide had a longer median time to tumor progression compared with those receiving placebo (14.3 vs. 6 months).(Rinke, Muller et al. 2009) Further support for the antiproliferative effect of somatostatin analogs in patients NET was demonstrated in the CLARINET trial, a randomized, placebo-controlled phase III trial evaluating the antiproliferative effects of lanreotide in patients with advanced well- or moderately-differentiated, non-functioning gastroenteropancreatic NETs, including both gastrointestinal NET and pancreatic NET. Patients receiving lanreotide had improved progression-free survival (PFS) compared to those receiving placebo (median not reached vs. median of 18 months).(Caplin, Pavel et al.

2014)

[figure not shown]
Agents targeting the VEGF- and mTOR-pathway signaling pathways are also active in the treatment of NET. In advanced pancreatic NET, independent randomized, placebo-controlled studies of everolimus and sunitinib demonstrated clear improvements in progression-free survival (PFS), leading to the approval of both agents for this indication.(Raymond, Dahan et al. 2011, Yao, Shah et al. 2011) In advanced carcinoid tumors, however, there remains no approved drug for tumor control, and the development of effective systemic therapy for this patient population represents a clear and unmet medical need.

### ***VEGF Inhibition in Carcinoid Tumors***

[figure not shown]
Several studies suggest that vascular endothelial growth factor (VEGF) pathway inhibition is a promising approach in treating patients with advanced carcinoid tumors. A key role for angiogenesis and VEGF pathway signaling in NET has been suggested by clinical observations that NET are vascular tumors. Additionally, pre-clinical studies have demonstrated that NET have increased expression of VEGF, VEGF receptor-2 (VEGFR-2), and other growth factor receptors including platelet-derived growth factor receptors (PDGFRs)  $\alpha$  and  $\beta$ , stem-cell factor receptor (c-kit).(Fjallskog, Lejonklou et al. 2003, Hansel, Rahman et al. 2003, Fjallskog, Hessman et al. 2007, Bowen, Silva et al. 2009, Silva, Bowen et al. 2011)

The VEGF pathway inhibitors bevacizumab, sunitinib, sorafenib, and pazopanib have been evaluated in advanced carcinoid tumors in the phase II setting.(Hobday, Rubin et al. 2007, Kulke, Lenz et al. 2008, Yao, Phan et al. 2008, Phan, Yao et al. 2010) These drugs have shown low radiographic response rates, but a relatively high rate of disease stabilization and encouraging median progression-free survival durations (8-14 months).

We have evaluated the prognostic significance of expression of VEGF pathway components, including VEGF-A, VEGFR-1, and VEGFR-2, in NET (Fig 1) and found that expression of VEGFR-2 appears to be an adverse prognostic factor associated with shorter overall survival (Fig 2).

**Figure 1: Expression of VEGF-A, VEGFR-1 and VEGFR-2 by immunohistochemistry.**

**Figure 2: Overall survival of patients with NET according to VEGFR2 expression.**

## 2.2 IND Agent

Ramucirumab has been previously evaluated as monotherapy in separate clinical studies, and a recommended schedule and dose range for monotherapy has been determined. Detailed information about the characteristics of ramucirumab is provided in the Investigator's Brochure (IB). The following sections provide a summary of the information most relevant to this phase II study.

### 2.2.1 Ramucirumab

#### *Mechanism of action:*

Ramucirumab (IMC-1121B [LY3009806]) is a human receptor-targeted monoclonal antibody that specifically binds VEGF Receptor 2. The binding of ramucirumab to VEGF Receptor 2 prevents its interaction with activating ligands (VEGF-A, VEGF-C, and VEGF-D). As a result, ramucirumab inhibits ligand-stimulated activation of VEGF Receptor 2 and its downstream intracellular signaling components, including Erk1/Erk2, neutralizing ligand induced proliferation and migration of human endothelial cells.

#### *Pharmacokinetics:*

Trough concentrations (or minimum concentrations [Cmin]) were collected in two Phase 3 studies (REGARD and RAINBOW) in patients with gastric cancer. Following the recommended clinical dose regimen, 8 mg/kg every 2 weeks, observed Cmin values were similar between

REGARD and RAINBOW, as noted in the table below (Investigator's Brochure, [Table 6.1](#)). The geometric mean observed trough values were approximately 50 ug/mL and approximately 60 to 70 ug/mL before the fourth and seventh doses, respectively.

**Table 6.1. Summary of Observed Ramucirumab Trough Concentrations for Patients with Advanced Gastric Cancer Following Administration of 8 mg/kg of Ramucirumab Every 2 Weeks as an IV Infusion over Approximately 1 Hour Alone (REGARD) or in Combination with Paclitaxel (RAINBOW)**

Dose Number	Trough a Serum Concentrations (ug/mL)			
	4		7	
	REGARD	RAINBOW	REGARD	RAINBOW
n PK	53	203	34	142
Geo Mean	49.5	45.0	74.4	62.8
Geo CV%	81	50	58	47

Abbreviations: CV% = percentage coefficient of variation; Geo = geometric; IV = intravenous; nPK = number of pharmacokinetic observations included in calculation.

a Trough concentrations were obtained prior to Doses 4 and 7. They also represent Cmin following Doses 3 and 6.

Pharmacokinetic data were from pooled from 8 studies including 497 patients with various malignancies for a population pharmacokinetic (PopPK) analysis. In these studies, ramucirumab was administered as a 1-hour I.V. infusion, at either 8 mg/kg once every 2 weeks on a 14- or 28-day cycle, or 10 mg/kg every 3 weeks on a 21-day cycle. The geometric mean (percentage coefficient of variation [CV%]) of PopPK model-derived estimates of ramucirumab clearance (CL), volume of distribution at steady state (Vss) and terminal half-life (t1/2) were 0.0140 L/h (29.8%), 5.5 L (14.4%), and 15 days (24.1%), respectively. These parameter estimates were consistent with those observed with other human monoclonal IgG1 (Keizer et al. 2010) antibodies. Results from the PopPK analyses indicate that the PK of ramucirumab following 8- and 10-mg/kg dose administrations were dose linear (absolute dose range: 169 to 1234 mg) and time independent.

Weekly doses of ramucirumab ranging from 2 to 16 mg/kg were evaluated in a Phase 1 study: I4TIE- JVBM [IMCL CP12-0401]. A maximum tolerated dose (MTD) for weekly dosing was identified as 13 mg/kg (2 dose-limiting toxicities [DLTs] were observed in patients receiving the 16-mg/kg weekly dose: Grade 3 deep vein thrombosis and Grade 3 hypertension). Preliminary activity was observed across a range of doses, including the 2-mg/kg dose. Pharmacokinetic results from this study suggested that, as with other recombinant human IgG1 monoclonal antibodies targeting cell membrane-expressed antigens, ramucirumab exhibited nonlinear PK characteristics.

Apparent nonlinear PK profiles were observed between 2 and 8 mg/kg; PK profiles appeared to be linear at and above 8 mg/kg, suggesting saturation of the target mediated (VEGF Receptor 2) clearance pathway. Every-2-week (6 to 10 mg/kg) and every-3- week (15 to 20 mg/kg) dose regimens were evaluated in an additional dose-ranging study (Study I4T-IE-JVBN [IMCL CP12-0402]). No MTD was identified for every-2-week or every-3-week dosing; all dose regimens were well tolerated, and preliminary evidence of clinical efficacy was observed across a range of dose/schedule cohorts.

*Clinical Experience and Activity:*

Ramucirumab has been studied and/or continues to be investigated in ongoing clinical studies for the indications as indicated in the Investigator's Brochure. As of 31 December 2013, ramucirumab or ramucirumab/placebo has been administered either as a single agent or in combination with various antineoplastic agents to approximately 7000 patients with different oncologic conditions in Phase 1/1b, Phase 2, and Phase 3 clinical trials.

Ramucirumab demonstrated significant and clinically meaningful benefit in overall survival (OS) as a single agent at a dose of 8 mg/kg every 14 days in patients with advanced gastric cancer in the REGARD study, a randomized Phase 3 trial of ramucirumab monotherapy with best supportive care [BSC] versus placebo with best supportive care.(Fuchs, Tomasek et al. 2014) Ramucirumab also has shown clinical efficacy in patients with gastric cancer in combination with paclitaxel in a phase III study of paclitaxel with ramucirumab compared with paclitaxel with placebo (RAINBOW).(Wilke, Muro et al. 2014) A Phase 3 trial (ROSE) examining the combination of ramucirumab with docetaxel in previously untreated metastatic breast cancer failed to meet its primary endpoint of investigator-assessed progression-free survival (PFS). In ROSE, while investigator-assessed PFS numerically favored ramucirumab, this difference was not statistically significant.(Mackey, Ramos-Vazquez et al. 2015)

Please refer to the current version of the Investigator's Brochure for updated information regarding the clinical experience and activity of ramucirumab.

*Adverse Events:*

As of 31 December 2013, AE information was available for 2485 patients receiving ramucirumab drug product (DP) on 7 Phase 1/1b studies, 18 open-label or unblinded Phase 2 studies, and 3 completed Phase 3 studies, including monotherapy and combination therapy with cytotoxic chemotherapy agents. Placebo-controlled blinded clinical trials are ongoing (1 Phase 2 study, 3 Phase 3 studies); unblinded safety data for these studies are not available. Detailed AE information based on a review of Phase 1/1b, Phase 2, and completed Phase 3 clinical studies of ramucirumab DP (N=2485) are available in the Investigator Brochure.

Adverse drug reactions (ADRs; AEs for which a causal relationship to the investigational drug was considered at least possible) of special interest include AEs which have been associated with antiangiogenic agents and therapeutic monoclonal antibodies and include the following categories: infusion-related reaction (IRR), hypertension, proteinuria, arterial thromboembolic events (ATEs), venous thromboembolic events (VTEs), bleeding/hemorrhagic events, gastrointestinal (GI) perforation, and congestive heart failure (CHF) when used in combination with mitoxantrone or following prior anthracycline therapy.

Infusion-related reaction is considered an adverse event of special interest (AESI), as it has been observed in association with other approved and investigational therapeutic monoclonal antibodies. With the exception of liver injury/liver failure, the AESIs discussed are potentially associated with other agents that inhibit VEGF- or VEGF Receptor 2-mediated angiogenesis.

Some AESIs also have been reported in clinical trials of ramucirumab DP, although in some instances a causal association with ramucirumab DP could not be clearly established. Liver failure and/or other significant liver injury events were included as an AESI in August 2012, following the independent data monitoring committee (IDMC) recommendations in an ongoing Phase 3 study in patients with advanced hepatocellular carcinoma (HCC; Study I4T-IE-JVBF [IMCL CP12-0919; REACH]).

Animal studies have not been specifically conducted to evaluate the effect of ramucirumab on female reproduction and fetal development, and there are no studies in pregnant women.

Please refer to Section 7 or the protocol and the current version of the Investigator's Brochure for updated information regarding the adverse events associated with ramucirumab.

### **2.3 Rationale**

Ramucirumab is a fully human monoclonal antibody targeting VEGFR-2 that prevents ligand binding and receptor-mediated pathway activation. In light of pre-clinical data demonstrating prognostic significance for VEGFR-2 expression in NET and preliminary evidence of activity of VEGF pathway inhibitors in carcinoid, we propose a 43 patient single-arm phase II study of ramucirumab in advanced carcinoid tumors. Because somatostatin analogs also have antitumor activity, concurrent treatment with a somatostatin analog will be required in all patients.

A future randomized, placebo-controlled phase II study or phase III study could be planned if ramucirumab demonstrates efficacy in this study.

Because prior studies of targeted agents have demonstrated low RECIST-defined tumor response rates in advanced carcinoid, we propose enrolling patients with documented disease progression and will use progression-free survival (PFS) as a primary endpoint. Assessment of efficacy will be made by comparing our results to the PFS of patients in the placebo arm of the RADIANT-2 study, a randomized phase III study of everolimus plus octreotide LAR vs. placebo plus octreotide LAR in patients with progressive carcinoid tumors with carcinoid syndrome.

We hypothesize that ramucirumab in combination with a somatostatin analog will be active in the treatment of advanced carcinoid tumors and will be associated with a median PFS duration of 12 months or greater.

## **3. PARTICIPANT SELECTION**

### **3.1 Eligibility Criteria**

3.1.1 Participants must have histologically or cytologically confirmed low- to intermediate-grade neuroendocrine tumor (carcinoid tumor).

- 3.1.2 Carcinoid tumors of any site are eligible. Patients with pancreatic neuroendocrine tumors are excluded.
- 3.1.3 Participants must have measurable disease, defined as at least one lesion that can be accurately measured in at least one dimension (longest diameter to be recorded for non-nodal lesions and short axis for nodal lesions) as  $\geq 20$  mm with conventional techniques or as  $\geq 10$  mm with spiral CT scan, MRI, or calipers by clinical exam. See Section 10 for the evaluation of measurable disease.
- 3.1.4 Locally advanced, unresectable or metastatic disease.
- 3.1.5 Patients must have evidence of radiographic disease progression within the past 12 months. Progressive disease by RECIST criteria is not required.
- 3.1.6 Age  $\geq 18$  years.
- 3.1.7 ECOG performance status 0-1 (see Appendix A).
- 3.1.8 Participants must have normal organ and marrow function as defined below:
- |                             |  |
|-----------------------------|--|
| - absolute neutrophil count | $\geq 1,000/\text{mm}^3$   |
| - platelets                 | $\geq 100,000/\text{mm}^3$   |
| - hemoglobin                | $\geq 9\text{ g/dL}$   |
| - total bilirubin           | $\leq 1.5 \times$ institutional upper limit of normal  |
| - AST(SGOT)/ALT(SGPT)       | $\leq 3 \times$ institutional upper limit of normal, or $\leq 5 \times$ institutional upper limit of normal in the setting of liver metastases   |
| - creatinine                | $\leq 1.5 \times$ upper limit of normal  |
| - urinary protein           | $\leq 1+$ on dipstick or routine urinalysis (if urine dipstick or routine urinalysis is 2+, a 24-hour urine collection for protein must demonstrate $<1000$ mg of protein in 24 hours)   |
| - coagulation function      | Adequate coagulation function as defined by International Normalized Ratio (INR) $\leq 1.5$ and a partial thromboplastin time (PTT) $< 1.5 \times$ institutional upper limit of normal. Patients on full-dose anticoagulation must be on a stable dose (minimum duration 14 days) of oral anticoagulant or low molecular weight heparin. |

3.1.9 The effects of ramucirumab on the developing human fetus are unknown. For this reason and because anti-angiogenic agents are known to be teratogenic, women of child-bearing potential and men must agree to use adequate contraception (hormonal or barrier method of birth control; abstinence) prior to study entry and for the duration of study participation. Should a woman become pregnant or suspect she is pregnant while she or her partner is participating in this study, she should inform her treating physician immediately. Men treated or enrolled on this protocol must also agree to use adequate contraception prior to the study, for the duration of study participation, and 4 months after completion of ramucirumab administration.

3.1.10 Ability to understand and the willingness to sign a written informed consent document.

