## **3.2 Exclusion Criteria**

- 3.2.1 Patients who have had chemotherapy or radiotherapy within 4 weeks prior to entering the study or those who have not recovered from adverse events due to agents administered more than 4 weeks earlier.
- 3.2.2 Patients who have undergone major surgery within 28 days or subcutaneous venous access device placement within 7 days prior to study enrollment.
- 3.2.3 Patients with elective or planned major surgery to be performed during the course of the clinical trial.
- 3.2.4 Patients who are receiving any other investigational agents.
- 3.2.5 Patients with any Grade 3-4 gastrointestinal bleeding within 3 months prior to enrollment.
- 3.2.6 Patients with a history of deep vein thrombosis, pulmonary embolism, or any other significant thromboembolism (venous port or catheter thrombosis or superficial venous thrombosis are not considered “significant”) during the 3 months prior to registration.
- 3.2.7 Patients who have experienced any arterial thromboembolic events, including but not limited to myocardial infarction, transient ischemic attack, cerebrovascular accident, or unstable angina, within 6 months prior to enrollment.
- 3.2.8 Patients with uncontrolled or poorly-controlled hypertension (>160 mmHg systolic or > 100 mmHg diastolic for >4 weeks) despite standard medical management.
- 3.2.9 Patients who have congestive heart failure (NYHA Class III or IV), sustained ventricular tachycardia, ventricular fibrillation, clinically significant bradycardia, advanced heart block within the six months preceding enrollment.

- 3.2.10 Patients who have cirrhosis at a level of Child-Pugh B (or worse) or cirrhosis (any degree) and a history of hepatic encephalopathy or clinically meaningful ascites resulting from cirrhosis.
- 3.2.11 Patients with a serious or nonhealing wound, ulcer, or bone fracture within 28 days prior to enrollment.
- 3.2.12 Patients receiving chronic antiplatelet therapy, including aspirin, nonsteroidal anti-inflammatory drugs (NSAIDs, including ibuprofen, naproxen, and others), dipyridamole or clopidogrel, or similar agents. Once-daily aspirin use (maximum dose 325 mg/day) is permitted.
- 3.2.13 Patients with uncontrolled brain or leptomeningeal metastases, including patients who continue to require glucocorticoids for brain or leptomeningeal metastases.

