### 6.3.5 Venous Thromboembolic Events

#### Grade 3 or asymptomatic Grade 4:

Interrupt ramucirumab. If the planned duration of full-dose anticoagulation is <2 weeks, protocol treatment should be held until the full-dose anticoagulation period is over. If the planned duration of full-dose anticoagulation is  $>2$  weeks, protocol treatment may be resumed during the period of full-dose anticoagulation if all of the following criteria are met:

- The patient must have an in-range INR (usually between 2-3) on a stable dose of warfarin (or other anticoagulant) prior to restarting therapy;
- The patient must not have had a grade 3 or 4 hemorrhagic event while on study; and
- The patient must not have had evidence of a tumor involving major blood vessels on any prior CT scan.

Patients with unresected primary tumors (or local recurrence) who develop Grade 3 and 4 venous thromboembolism may also receive anticoagulation and continue ramucirumab therapy provided that the tumor does not confer an excessive bleeding risk, in the opinion of the patient's physician.

For recurrent/worsening venous thromboembolic events after resumption of treatment:  
Discontinue ramucirumab.

For symptomatic grade 4:  
Discontinue ramucirumab.

Any venous thrombotic event leading to discontinuation of ramucirumab therapy will be considered serious and should be reported via the SAE mechanism.

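### Section 3.1.8 lets a patient on stable full-dose anticoagulation start ramucirumab with no written check on tumor involving major vessels or tumor bleeding risk, both of which Section 6.3.5 uses after an on-study venous clot

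*Combined protocol and SAP*

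**What the plan says.** **At entry.** The coagulation row of Section 3.1.8 requires INR of at most 1.5 and PTT below 1.5 times the upper limit of normal. It then adds: "Patients on full-dose anticoagulation must be on a stable dose (minimum duration 14 days) of oral anticoagulant or low molecular weight heparin". It does not restrict the reason for anticoagulation and attaches no condition about the tumor. Section 3.1.2 admits carcinoid of any site except pancreas. Section 3.1.4 admits "Locally advanced, unresectable or metastatic disease". Section 3.2.6 excludes significant thromboembolism only in the 3 months before registration, and "venous port or catheter thrombosis or superficial venous thrombosis are not considered" significant.

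**After an on-study clot.** Section 6.3.5 interrupts ramucirumab for a Grade 3 or asymptomatic Grade 4 venous event. If full-dose anticoagulation is planned for less than 2 weeks, treatment waits until it ends. If it is planned for more than 2 weeks, "protocol treatment may be resumed during the period of full-dose anticoagulation if all of the following criteria are met". The listed criteria are an in-range INR (usually 2 to 3) on a stable anticoagulant dose, no Grade 3 or 4 hemorrhage on study, and this: "The patient must not have had evidence of a tumor involving major blood vessels on any prior CT scan". A further paragraph says that patients with an unresected primary or local recurrence and a Grade 3 or 4 event "may also receive anticoagulation and continue ramucirumab therapy provided that the tumor does not confer an excessive bleeding risk", in their physician's opinion.

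**The concern.** Sections 2.2.1 and 7.1.1 both list bleeding among the events associated with ramucirumab. Full-dose anticoagulation adds to that risk, and tumor involving a large vessel is where a bleed could be most serious. In 6.3.5 the plan recognises that anatomy matters when the two treatments are combined, and asks for it to be checked before ramucirumab is resumed. At the first dose, where the same combination can occur, nothing written asks for the check.

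The stake is patient safety: an avoidable serious hemorrhage in an anticoagulated patient whose baseline scan already showed the problem. Eligibility under Section 4.1 rests on an investigator confirming the criteria and a study team member completing a protocol-specific checklist. If the criteria do not mention an item, that process gives no prompt for it.

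**Working it through.** The plan gives no figure on this point, so the check is a comparison of texts.

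1. **Can a patient on full-dose anticoagulation enter?** Yes; 3.1.8 provides for it. Read literally, the INR limit of 1.5 keeps out patients on therapeutic warfarin, whose range 6.3.5 gives as usually 2 to 3. Patients on low molecular weight heparin, which the sentence names, can still enter if INR and PTT are within limits. If the anticoagulation sentence is instead read as an exception to the INR limit, warfarin patients enter too and the gap is wider. It exists on either reading.

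2. **Does the thrombosis exclusion close the route?** No. Section 3.2.6 reaches back only 3 months and does not count port, catheter or superficial venous thrombosis.

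3. **Is there a written tumor check at entry?** Sections 3.1, 3.2, 5.2 and the Section 9 calendar were read for either consideration. Neither appears. Both are found only in 6.3.5.

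| | Entry, 3.1.8 | After on-study venous event, 6.3.5 |
|---|---|---|
| Full-dose anticoagulation with ramucirumab | Allowed | Allowed under conditions |
| Stable anticoagulant dose | Required, 14 days | Required |
| Tumor involving major vessels | Not mentioned | Bars resumption under the list for courses planned over 2 weeks |
| Tumor bleeding risk | Not mentioned | Physician judgement, for unresected primary or local recurrence |

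4. **Do other entry controls cover it?** They lower bleeding risk in general:
   - 3.1.8: platelets of at least 100,000
   - 3.2.5: Grade 3-4 gastrointestinal bleeding within 3 months
   - 3.2.12: chronic antiplatelet and NSAID use, with once-daily aspirin up to 325 mg allowed
   - 3.2.13: uncontrolled brain or leptomeningeal metastases
   - 3.2.16: a general clause on other conditions

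   None of these names tumor anatomy in an anticoagulated patient. Section 3.2.5 would exclude a patient whose tumor had recently bled seriously into the gut, but not one whose tumor has yet to bleed.

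5. **Do later controls cover it?** The review of the first 10 patients (5.1, 12.4), committee review (11.2) and discontinuation for Grade 3 or 4 bleeding (6.3.7) all act after exposure.

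6. **Is the information available before Day 1?** Yes. Section 9, footnote b, requires baseline arterial and venous phase CT of chest, abdomen and pelvis, or an equivalent modality, within 28 days before treatment.

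7. **How many patients?** The documents give neither the share on full-dose anticoagulation nor the share with vessel involvement. One patient would be 1/43 = 2.3% of the planned sample; that is a unit of scale, not an estimate.

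**The case against.** The strongest answer is that the two settings differ. Section 6.3.5 deals with a new clot that occurred on ramucirumab. Section 3.1.8 deals with a patient already stable on anticoagulation, with no significant thromboembolism in the past 3 months. Tighter rules after an event on the drug are normal. This stands, and it rules out one tempting inference, that the protocol contradicts itself. It does not fully explain the vessel criterion, because vessel involvement is a feature of the tumor and is present whether or not a clot has occurred.

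A reader might also infer that the plan would always stop after a clot the very patient it admits at entry. The text does not support that. The vessel item belongs to the list for courses planned for more than 2 weeks. The paragraph on unresected primary or local recurrence can be read as a separate permission resting on physician judgement. All that can be said is that such a patient would fail the restart list.

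Nor does the text show that entry has no bleeding protection, or that nobody looks at the baseline scan. Several exclusions bear on bleeding, and the examples in 3.2.16 are not exhaustive, so an investigator could use that clause. What is missing is a written prompt.

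Finally, the documents hold no data on bleeding by vessel involvement in anticoagulated patients given ramucirumab. That is correct. The support is the plan's own use of the criterion in a neighbouring setting, together with bleeding being a listed risk.

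**Conclusion.** The point holds as a gap in the written entry criteria. Following the plan as written, a patient on low molecular weight heparin with INR and PTT within limits, and with tumor involving a major vessel on the baseline scan, could be dosed on Day 1 without any documented consideration of that finding.

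The size is unknown. The number affected cannot be derived from the documents and may be zero, since a patient must be on full-dose anticoagulation, meet the laboratory limits and have vessel involvement. The primary PFS analysis, sample size and power are unaffected. The conclusion assumes that the eligibility checklist, which is not part of the documents, follows the written criteria and adds no such item. It is a cheap safety improvement worth making, not a fault in the design.

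**What to change.** Add to 3.1.8, and as one line in the eligibility checklist:

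*A patient on full-dose anticoagulation may enter only if neither the baseline scan nor any earlier CT (or an equivalent modality accepted in Section 9) shows tumor involving major blood vessels. A patient with an unresected primary tumor or a local recurrence may enter if the investigator judges, and documents, that the tumor does not carry an excessive risk of bleeding.*

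The second sentence keeps the latitude that 6.3.5 gives for these patients, which matters because 3.1.4 admits locally advanced, unresectable disease. Patients not on full-dose anticoagulation are untouched. Section 6.3.5 does not define which vessels are major or what counts as involvement. The same amendment could define both terms for the two sections.

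The cost is a short protocol amendment and a checklist line. No new test is needed. Some anticoagulated patients, an unknown but probably small number, would become ineligible.
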